8.2. Setting

Patients with HR+/HER2- ABC within the US and CAN will be enrolled from a geographically representative population as well as from diverse treatment settings (e.g., academic and community sites). ABC patients whose treatment decision with palbociclib has been made by their treating physician and meet the eligibility criteria will be invited to participate in the study. Eligibility will be assessed at the date of the enrollment visit (i.e. Baseline/Visit 1).

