2. Follow up through End of Study: Enter data at SOC visits where each subsequent (post palbociclib treatment) MBC treatment regimen is prescribed and at end of study.
3. Breast cancer treatment: including surgery, radiation, systemic chemotherapy, hormone therapy, and/or targeted therapy, in both neoadjuvant/adjuvant and metastatic disease settings, prior to, during, and post palbociclib treatment; supportive care is also collected in the metastatic setting while on this study.
4. Physician MBC Treatment Selection Survey: Treating physicians will complete a treating physician MBC treatment selection survey that will capture the reason(s) for treatment choice at start of palbociclib therapy and at start of subsequent therapies.
5. Clinical assessments: overall clinical response as judged by treating physician, at intervals per standard of care schedule: imaging assessment, clinical progression, and clinical biomarkers.

CCI

7. CBC: Baseline and during palbociclib treatment, enter any CBC during the 1st 3 cycles, then enter Day 1 (or prior to start of a new cycle) CBC for the subsequent cycles as per standard of care.

8. AE/SAE reporting begins at the time of the patient's first dose of palbociclib or the time of the patient's informed consent if s/he is already exposed to palbociclib and up to 28 calendar days following the last administration of palbociclib.

Table 2: EORTC QLQ-C30 and Geriatric Assessments

Data Collection and Entry	Baseline	Through End of Treatment with Palbociclib
	► SOC Visit 1	
EORTC QLQ-C30 ¹	x ¹	x ¹
G8 Screening Tool ²	x ²	x ²
ADL: Activities of Daily Living ²	x ²	x ²

ADL = Activities of Daily Living; EORTC QLQ-C30 = European Organisation for the Research and Treatment of Cancer Quality of Life Questionnaire Core 30

1. EORTC QLQ-C30 will be collected at baseline (before starting palbociclib) then monthly for the first 3 months of treatment with palbociclib, then every three months until the end of treatment with palbociclib.

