Participation in this study is not intended to change the routine treatment patients receive, as determined by their prescribing physicians; all treatment decisions, type, and timing of disease monitoring are at the discretion of the treating physician and patient. Assessments include patient questionnaires and quality of life (EORTC QLQ-C30, G8 Screening Tool,

PFIZER CONFIDENTIAL

Activities of Daily Living [ADL] Questionnaire), site questionnaires, physician metastatic breast cancer (MBC) treatment selection survey, and **CCI** [REDACTED].

Baseline (or Visit 1) is defined as the date of study enrolment when informed consent is obtained and inclusion/exclusion criteria assessed. The Data Entry Schedule is included in Table 1 and the EORTC QLQ-C30 and Geriatric Assessments in Table 2.

Table 1: Data Entry Schedule

Data Collection and Entry ¹	►	Baseline	During Treatment with Palbociclib	Post Treatment with Palbociclib
		SOC Visit 1	SOC Visit 2 through End of Treatment with Palbociclib	Follow-up through End of Study ²
Informed Consent & Inclusion/Exclusion Criteria		x		
Patient Demographics, Study Site Characteristics, Medical History, Baseline Concomitant Medications, Baseline Metastatic Disease Status		x		
Breast Cancer Diagnosis and Recurrence History		x		
Breast Cancer Treatment ³		x ³	x ³	x ³
Physician MBC Treatment Selection Survey ⁴		x ⁴	x ⁴	x ⁴
Performance Status (ECOG)		x	x	
Clinical Assessments ⁵		x ⁵	x ⁵	x ⁵
CCI				
Laboratory: CBC ⁷		x ⁷	x ⁷	
Adverse Events and Serious Adverse Events ⁸		x ⁸	x ⁸	

SOC = Standard of care; ABC = advanced breast cancer; CBC = complete blood count; ECOG = Eastern Cooperative Oncology Group; MBC = metastatic breast cancer; SAE = serious adverse event

1. Data is collected in accordance with normal standard of care visits, enter all data available per Data Entry Schedule into the electronic data capture system.

2. Follow up through End of Study: Enter data at SOC visits where each subsequent (post palbociclib treatment) MBC treatment regimen is prescribed and at end of study.

3. Breast cancer treatment: including surgery, radiation, systemic chemotherapy, hormone therapy, and/or targeted therapy, in both neoadjuvant/adjuvant and metastatic disease settings, prior to, during, and post palbociclib treatment; supportive care is also collected in the metastatic setting while on this study.

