4. Physician MBC Treatment Selection Survey: Treating physicians will complete a treating physician MBC treatment selection survey that will capture the reason(s) for treatment choice at start of palbociclib therapy and at start of subsequent therapies.

5. Clinical assessments: overall clinical response as judged by treating physician, at intervals per standard of care schedule: imaging assessment, clinical progression, and clinical biomarkers.

CCI

7. CBC: Baseline and during palbociclib treatment, enter any CBC during the 1st 3 cycles, then enter Day 1 (or prior to start of a new cycle) CBC for the subsequent cycles as per standard of care.

8. AE/SAE reporting begins at the time of the patient's first dose of palbociclib or the time of the patient's informed consent if s/he is already exposed to palbociclib and up to 28 calendar days following the last administration of palbociclib.

Table 2: EORTC QLQ-C30 and Geriatric Assessments

Data Collection and Entry	Baseline	Through End of Treatment with Palbociclib
	SOC Visit 1	
EORTC QLQ-C30 ¹	x ¹	x ¹
G8 Screening Tool ²	x ²	x ²
ADL: Activities of Daily Living ²	x ²	x ²

ADL = Activities of Daily Living; EORTC QLQ-C30 = European Organisation for the Research and Treatment of Cancer Quality of Life Questionnaire Core 30

1. EORTC QLQ-C30 will be collected at baseline (before starting palbociclib) then monthly for the first 3 months of treatment with palbociclib, then every three months until the end of treatment with palbociclib.

2. G8 Screening Tool and Activities of Daily Living to be completed only for patients equal to or greater than 70 years of age at the time of study enrollment. G8 and ADL will be collected at baseline (before starting palbociclib) then monthly for the first 3 months of treatment with palbociclib, then every three months until the end of treatment with palbociclib. ADL to be completed by the patient or in conjunction with the appropriately delegated site staff, G8 to be completed by the treating physician or the appropriately delegated site staff.

PFIZER CONFIDENTIAL

STUDY OBJECTIVES

The objectives of this prospective NIS of palbociclib in ABC treatment are:

- Palbociclib prescribing and treatment patterns in routine clinical practice in ABC treatment;
- Clinical outcomes;
- MBC treatment sequence prior to, during, and after palbociclib ;

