8 STATISTICAL ANALYSIS

This study has a convenience sample; thus, results may not be generalizable to the entire population with the disease. Due to the study's exploratory nature, study measures will be summarized descriptively. Furthermore, any p value reporting should be placed in a descriptive framework for hypothesis generation and any such inferential analysis is intended to guide further research.

All analyses will be conducted using SAS® version 9.4 or higher.

The intention is to analyze all available data. In the advent that COVID may cause gaps in subject data or require adjustments to statistical methodologies, our intent is to address such issues if or as needed. Both ICON and Pfizer have internal guidances and recommendations on file to assist with decision-making with regards to COVID-related data issues and these will be consulted if or as needed.

GENERAL METHODS

For continuous variables, means, standard deviations (SD), medians, minimums, maximums, and missing will be reported. For discrete variables, frequencies and percentages will be reported. Missing or unknown categories for each variable also will be presented. Percentages will be calculated excluding missing or unknown values. 95% Confidence Intervals (CI) are two-sided.

All summaries will be performed for all patients in the corresponding analysis set and by treatment combination defined at study entry within the corresponding analysis set:

- Palbociclib + Letrozole or Anastrozole
- Palbociclib + Fulvestrant
- Palbociclib + Exemestane
- Other

The baseline record is defined as the last observed measurement prior to palbociclib administration. Change from baseline is defined as the post-baseline value minus the baseline value.

Time in days between two dates will be calculated using the formula most recent date minus earlier date plus 1. For time in months, the same formula for days will be applied but then divided by 30.4. For time in years, the same formula for days will be applied but then divided by 365.25.

Variable definitions are found in Appendix 1 Data Derivation Details.

DISPOSITION OF SUBJECTS

A subject disposition summary will be reported. Subjects' study completion date and reason for premature termination will be reported in listing format. Number of subjects with initial diagnosis and with recurrent diagnosis will be reported in table and listing format.

DEMOGRAPHIC AND BASELINE CLINICAL CHARACTERISTICS

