APPENDIX 1: DERIVED DATA DETAILS

Study End Date: the earliest of study withdrawal date or last contact visit date

Study Duration: defined in days as study end date minus baseline date +1.

Study Day: post-baseline visit or event date minus baseline date +1. For pre-baseline visits or events, study day is defined as pre-baseline visit or event date minus baseline date. Note there is no study equal to 0.

Age at baseline: defined in years as baseline date minus date of birth +1 divided by 365.25.

Duration of disease: defined in days from initial diagnosis date to study enrollment date.

Duration of ABC/MBC disease: defined in days from ABC/MBC diagnosis date to study enrollment date.

Disease-free interval: time from the end of adjuvant/neoadjuvant treatment to the first disease recurrence.

Paloma-3 disease-free interval: defined in days as the time between first diagnosis of breast cancer and onset of metastatic disease or disease recurrence.

Treatment-free interval: defined in days as the time from last dose of prior chemotherapy to first MBC therapy or first study dose whichever occurred earlier.

Line of Therapy (LOT):

Clinical outcome endpoints will be summarized by LOT which is defined based on the number of therapies taken after initial diagnoses of ABC or MBC, but before palbociclib treatment start:

- 1st line: patients had no LOT in the ABC/MBC setting before palbociclib initiation
- 2nd line: patients had one LOT in the ABC/MBC setting before palbociclib initiation
- 2⁺ line: patients had >1 LOT in the ABC/MBC setting before palbociclib initiation

Best Tumor Response: best overall tumor response recorded from palbociclib treatment start until first documentation of progressive disease. Only response assessments recorded on or before the start date of next subsequent line of treatment will be considered.

Clinical Benefit: a best overall tumor response of complete response or partial response at any time, or stable disease for at least 24 weeks post-study treatment initiation. Only response assessments recorded on or before the start date of next subsequent line of treatment will be considered.

Overall Survival (OS): is defined as time (months) from initiation of the palbociclib combination treatment to date of death, due to any cause.

First Hormonal Therapy After Stage III or IV Diagnosis: the first recorded MBC or adjuvant hormonal therapy after initial diagnosis of stage IIIb or IV MBC or ABC.

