APPENDIX 2: LAB VISIT WINDOWING

Visit	Visit Day	Window of Days	
		non-lab domains	CBC Labs
Baseline	1	<=1	
Day 15	15	n/a	2-18
Day 21	21	n/a	19-25
Day 28	28	n/a	26-45
Month 1	30	2-45	n/a
Month 2	60	46-75	
Month 3	90	76-135	
Month 6	180	136-225	
Month 9	270	226-315	
Month 12	360	316-405	
Month 15	450	406-495	
Month 18	540	496-585	
Month 21	630	586-675	
Month 24	720	676-765	
Month 27	810	766-XX	

If multiple records are assigned per analysis visit, the latest record will be selected for reporting.

An alternate presentation of lab data will display by Cycle. Cycle x is defined as any lab record between Cycle x start date until Cycle $x+1$ start date.

PFIZER CONFIDENTIAL

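### The SAP ties the baseline record to the first palbociclib dose, but its visit windows tie Baseline to enrolment, so the two pick different records for patients who start before or after consent

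*SAP*

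**What the plan says.** The SAP has one explicit rule for the baseline value. Section 8, General Methods: "The baseline record is defined as the last observed measurement prior to palbociclib administration". The next sentence there defines change from baseline from that record. SAP section 6 and the footnotes to Table 2 in both documents agree with it: they place the baseline questionnaires before palbociclib starts.

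Three other places build a different anchor:

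- SAP section 3, Study Design: "Baseline (or Visit 1) is defined as the date of study enrolment when informed consent is obtained and inclusion/exclusion criteria assessed".
- SAP Appendix 1: "Study Day: post-baseline visit or event date minus baseline date +1".
- SAP Appendix 2: the Baseline row is visit day 1 with a window of day 1 or earlier, and "If multiple records are assigned per analysis visit, the latest record will be selected for reporting". No condition on exposure is attached.

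Both documents foresee patients who have started palbociclib before enrolment. In footnote 8 of protocol Table 1, safety reporting starts at "informed consent if s/he is already exposed to palbociclib"; SAP Table 1 and protocol section 10 say the same. The eligibility criteria (protocol 8.2.1 and 8.2.2) ask that palbociclib be judged indicated and do not exclude patients who have begun it. The quality-of-life analysis set equals the full analysis set (SAP section 5), so these patients stay in.

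**The concern.** The two anchors agree only if nobody takes palbociclib before enrolment and no measurement falls between enrolment and first dose. The documents guarantee neither, and nowhere say which anchor prevails.

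Change from baseline is a planned summary for laboratory values (SAP 8.8.2), QLQ-C30 (8.9.1), ADL (8.9.2) and G8 (8.9.3). It also defines the 10-point worsening category in Appendix 1, and paired t-test p-values are to be reported for QLQ-C30. Two programmers, one following General Methods and one following Appendix 2, could use different records and different patients in these tables.

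**Working it through.** The plan states no figure on this point to reproduce. The check applies both rules to example first-dose dates.

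**Inputs**

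- Study day on or after enrolment = date − enrolment date + 1 (SAP Appendix 1, with the baseline date from Study Design).
- CBC windows (Appendix 2): Baseline ≤1, Day 15 = 2–18.
- Non-laboratory windows: Baseline ≤1, Month 1 = 2–45, Month 2 = 46–75, Month 3 = 76–135.
- No study-specific activity before consent (protocol 9.1), so no study questionnaire can predate enrolment.

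**Already on palbociclib at consent** (first dose 14, 28 or 60 days before enrolment)

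- The questionnaire completed at enrolment is on study day 1. Appendix 2 files it as Baseline, although it is on-drug.
- Under General Methods it does not qualify and no earlier study form can exist. There is no baseline and so no change score.
- A pre-palbociclib CBC may exist in the chart. If an on-drug CBC was also taken by day 1, the latest-record rule in Appendix 2 selects that one instead.

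**Starting after consent**

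| First dose | CBC taken the day before | General Methods | Appendix 2 |
|---|---|---|---|
| 7 days after enrolment (study day 8) | study day 7 | baseline | Day 15 window |
| 14 days after enrolment (study day 15) | study day 14 | baseline | Day 15 window |

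- The pre-dose CBC is then reported as the Day 15 value unless a later one falls by study day 18.
- The alternative by-cycle display is not affected. It runs from each cycle's start date, so a CBC before cycle 1 enters no cycle.
- A single pre-dose questionnaire dated after consent, on day 2 to 45, is filed under Month 1. Appendix 2 then has no Baseline form, so the change is missing, not zero.

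**Post-baseline windows**

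The questionnaire schedule follows months of palbociclib treatment (footnotes to Table 2). For a patient whose first dose was 60 days before enrolment, treatment day = study day + 60. The Month 1 window (2–45) therefore covers treatment days 62 to 105, which belong to Months 2 and 3 if counted from first dose. Correcting the Baseline row alone would leave this mismatch.

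**Number affected, illustration only**

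The share already exposed at consent, f, is not in the documents. With 1500 planned patients, 1500 × f gives:

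| Assumed f | Patients |
|---|---|
| 5% | 75 |
| 10% | 150 |
| 20% | 300 |
| 30% | 450 |

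Each would have an on-drug questionnaire baseline under Appendix 2 and none under General Methods. For G8 and ADL only those aged 70 or over count. The true f could be near zero.

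**The case against.** The strongest reply is that the SAP already has its rule. Study Design defines a date and a visit, not a value. Only General Methods defines a baseline record, and the questionnaire sections agree with it. The competing rule has to be assembled from the Study Design date, the Study Day definition and one row of an appendix headed for laboratory visits. Sections 8.9.1 to 8.9.3 already limit change summaries to patients with both values, so those without a baseline drop out. All of this stands, and it makes General Methods the natural rule to keep.

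It does not remove the conflict. Appendix 2 has a column for non-laboratory domains, and section 8.8.2 sends the laboratory analysis to that appendix. Day 1 might be read as the first dose, but the SAP never says so, and the only day count it defines runs from the baseline date. Followed as written, the windows select records that General Methods would not.

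A reader might also infer that both mismatches pull the estimated change toward zero by a calculable percentage. The documents do not support that:

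- An on-drug baseline understates a change only if the change before consent persists in the same direction. No trajectory is given for any scale. If an early change reverses, an on-drug baseline could create or reverse an apparent effect.
- A near-zero questionnaire change in late starters needs two pre-dose forms, and the schedule provides one.
- On-drug enrolment appears only as a condition in the safety-reporting text, with no frequency.

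**Conclusion.** The conflict is real and should be resolved before the change-from-baseline tables are programmed. It determines which records, and for questionnaires which patients, enter the change and worsening summaries. Its reach is limited:

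- The number of patients affected is unknown and could be small. The counts of 75 to 450 rest on assumed shares of 5% to 30%.
- The direction of any distortion is not established for any measure.
- For laboratory data in late starters, only the day-window display is exposed.
- Tumour response, rwPFS and OS run from palbociclib initiation (SAP section 8, Clinical Outcomes), so their time origin does not depend on the baseline rule.

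The study is descriptive and its primary goal is prescribing and treatment patterns, so this does not threaten its main purpose. A descriptive change score still needs one reproducible baseline.

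**What to change.** 1. Apply the General Methods rule everywhere: the baseline value is the last record before the first palbociclib dose. A record on the day of first dose counts only if taken before that dose.
2. Count all Appendix 2 windows, Baseline and every post-baseline row, from the first-dose date for both CBC and questionnaires. A treatment-day variable, separate from the Appendix 1 Study Day, would do this.
3. Keep the enrolment date for age, demographics and study duration, and say so in Study Design and Appendix 1.
4. Report how many patients were already exposed at consent and how many of them have no pre-dose record. State that patients without a pre-dose record leave the change-from-baseline and worsening summaries, as 8.9.1 to 8.9.3 already imply for change scores, and stay in the by-visit summaries.

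The work is SAP wording and one derivation. The first-dose date is already needed for rwPFS and OS. The real cost is that the change-from-baseline tables lose every patient without a pre-dose record. That may be more than a few if many were enrolled on drug: on the illustrative shares, up to 450 of 1500 for QLQ-C30.

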8.3. Variables

Patient demographics, study site characteristics, medical history, baseline concomitant medications, breast cancer diagnosis and recurrence history, metastatic disease status, MBC treatment, disease status and characteristics, performance status (ECOG), palbociclib dosing and treatment management, routine clinical efficacy assessment, physician MBC treatment selection survey, quality of life, geriatric screening tool and questionnaire, and **CCI** [REDACTED] will be assessed. Detailed definitions of variables that will be collected or derived for statistical analyses and summaries will be included in the Statistical Analysis Plan (SAP).

Data collected will be from the treating physicians' routine clinical assessments as per their local standard of care. Patients will be asked to complete the EORTC QLQ-C30; the G8 Geriatric Screening Tool and ADL will be completed for patients greater than or equal to 70 years of age at the time of study enrollment. The G8 Screening Tool will be completed by the treating physician or appropriately delegated site staff and the ADL will be completed by the patient or in conjunction with the appropriately delegated site staff. **CCI** [REDACTED]
[REDACTED]
[REDACTED]
[REDACTED]

The Data Entry Schedule is provided in Table 1 and the EORTC QLQ-C30 and Geriatric Assessments in Table 2.

Table 1: Data Entry Schedule

Data Collection and Entry¹	►	Baseline	During Treatment with Palbociclib	Post Treatment with Palbociclib
		SOC Visit 1	SOC Visit 2 through End of Treatment with Palbociclib	Follow-up through End of Study²
Informed Consent & Inclusion/Exclusion Criteria		x		
Patient Demographics, Study Site Characteristics, Medical History, Baseline Concomitant Medications, Baseline Metastatic Disease Status		x		
Breast Cancer Diagnosis and Recurrence History		x		
Breast Cancer Treatment ³		x ³	x ³	x ³
Physician MBC Treatment Selection Survey ⁴		x ⁴	x ⁴	x ⁴
Performance Status (ECOG)		x	x	
Clinical Assessments ⁵		x ⁵	x ⁵	x ⁵
CCI		█	█	
Laboratory: CBC ⁷		x ⁷	x ⁷	
Adverse Events and Serious Adverse Events ⁸		x ⁸	x ⁸	

SOC = Standard of care; ABC = advanced breast cancer; CBC = complete blood count; ECOG = Eastern Cooperative Oncology Group; MBC = metastatic breast cancer; SAE = serious adverse event

1. Data is collected in accordance with normal standard of care visits, enter all data available per Data Entry Schedule into the electronic data capture system.

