An investigator's causality assessment is the determination of whether there exists a reasonable possibility that palbociclib caused or contributed to an adverse event. If the investigator's final determination of causality is "unknown" and s/he cannot determine whether palbociclib caused the event, the safety event must be reported within 24 hours.

If the investigator cannot determine the etiology of the event but s/he determines that palbociclib did not cause the event, this should be clearly documented on the eCRF and the NIS AEM Report Form.

DEFINITIONS OF SAFETY EVENTS

Adverse events

An AE is any untoward medical occurrence in a patient administered a medicinal product. The event need not necessarily have a causal relationship with the product treatment or usage. Examples of adverse events include but are not limited to:

- Abnormal test findings (see below for circumstances in which an abnormal test finding constitutes an adverse event);
- Clinically significant symptoms and signs;
- Changes in physical examination findings;
- Hypersensitivity;
- Lack of efficacy;
- Drug abuse;
- Drug dependency.

Additionally, for medicinal products, they may include the signs or symptoms resulting from:

- Drug overdose;
- Drug withdrawal;
- Drug misuse;
- Off-label use;
- Drug interactions;
- Extravasation;
- Exposure during pregnancy;
- Exposure during breast feeding;
- Medication error;
- Occupational exposure.

Abnormal test findings

The criteria for determining whether an abnormal objective test finding should be reported as an adverse event are as follows:

- Test result is associated with accompanying symptoms, and/or
- Test result requires additional diagnostic testing or medical/surgical intervention, and/or
- Test result leads to a change in study dosing or discontinuation from the study, significant additional concomitant drug treatment, or other therapy, and/or
- Test result is considered to be an adverse event by the investigator or sponsor.

Merely repeating an abnormal test, in the absence of any of the above conditions, does not constitute an adverse event. Any abnormal test result that is determined to be an error does not require reporting as an adverse event.

Serious adverse events

A serious adverse event is any untoward medical occurrence in a patient administered a medicinal or nutritional product (including pediatric formulas) at any dose that:

- Results in death;

- Is life-threatening;

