Demographic and baseline characteristics variables will be summarized for the FAS. For continuous variables (i.e., age at study enrollment, weight, height, BMI), summary statistics will be generated. For categorical variables (sex, race, ethnicity, insurance provider), the frequency and percentage of subjects in each category will be presented.

The following disease-related baseline characteristics will be summarized:

- Paloma-3 disease-free interval
- Disease free interval following treatment for early stage disease
- Treatment-free interval
- ABC/MBC diagnosis
- Duration of ABC/MBC disease
- Age of diagnosis
- Disease type
- Disease stage
- Disposition of diagnosis
- Performed biopsy and associated mutations
- Diagnostic imaging performed and imaging method
- Sites of metastases
- Estrogen Receptor (ER)/Progesterone receptor (PR) status
- Human epidermal growth factor receptor 2 (HER2) status
- Visceral status
- ECOG performance status
- Line of therapy in the ABC/MBC setting (1st line, 2nd line, 2+ line)
- Menopause status

MEDICAL HISTORY AND CONCURRENT MEDICAL CONDITIONS

Medical history and concurrent medical conditions will be summarized and presented in tabular and listing format for the FAS.

In addition, the CCI score^{17, 18} will be calculated. See Appendix 1 Data Derivation Details. Note cancer will not be included in the CCI calculation because it is the diagnosis of interest. CCI score at time of enrolment will be summarized and reported in tabular format.

MEDICATION HISTORY AND CONCOMITANT MEDICATION

Summarized information on medication history for the FAS will include:

- Prior therapy for initial diagnosis and the best response
- Prior therapy at ABC/MBC setting and the best response
 - Number of Lines of therapy
 - Therapy categories
 - Best response
- Prior chemotherapy
- Treatment free interval
- Prior radiation therapy
- Months from last prior radiation to first study dose
- Prior surgery or non-radiation procedures

All concomitant medications will be coded by therapeutic classification, subclassification, and medication using the World Health Organization Drug Dictionary (WHO Drug). A concomitant medication is defined as a medication that is ongoing as of Study Day 1, ends on or after Study Day 1, or starts on or after Study Day 1 and no more than 28 days after the last dose of study drug.

Concomitant medication of interest will be reported separately.

STUDY DRUG EXPOSURE

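### The SAP's concomitant-medication window runs to 28 days after the last dose, but outside supportive care the data entry schedule collects these medications at baseline only

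*SAP*

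**What the plan says.** **What will be analysed.** SAP Section 8, under Medication History and Concomitant Medication, states "All concomitant medications will be coded by therapeutic classification, subclassification, and medication". A medication qualifies if it is ongoing on Study Day 1, ends on or after that day, or "starts on or after Study Day 1 and no more than 28 days after the last dose of study drug". The section adds: "Concomitant medication of interest will be reported separately". No list of those medications is given. By SAP Appendix 1 and the Study Design text, Study Day 1 is the enrolment date.

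**What will be collected.** The variable list in Protocol Section 8.3 reads "medical history, baseline concomitant medications, breast cancer diagnosis and recurrence history". Protocol Table 1 has one row that mentions concomitant medications, and it is marked in the baseline column only. SAP Table 1 repeats the row, "Medical History, Baseline Concomitant Medications, Baseline Metastatic Disease Status", with the same single mark. Footnote 1 tells sites to "enter all data available per Data Entry Schedule into the electronic data capture system".

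**What is collected later.** The breast cancer treatment row is marked in all three periods. Its footnote 3 covers anticancer treatment and adds that "supportive care is also collected in the metastatic setting while on this study". Separately, Protocol Section 10 asks for relevant concomitant medications when serious or 24-hour reportable safety events are followed up.

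**The concern.** The SAP definition needs start dates for drugs begun at any time from enrolment to 28 days after the last palbociclib dose. The schedule in the same SAP, and in the protocol, asks sites for general medications once, at Visit 1. A site that follows Table 1 enters an anticoagulant taken at enrolment but is not asked for the same drug if it is started two months later.

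The resulting gap cannot be seen in the data. A field that is requested and left blank shows up as missing, and SAP Section 8 presents missing categories. A drug that no form requests leaves no record at all, so the patient is counted as not taking it. A reader who takes the output at its stated definition would read a figure drawn mainly from one visit as use over the whole treatment period.

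**Working it through.** The documents state no medication rate, so there is no plan figure to reproduce. The check is a comparison of texts, followed by an illustration with assumed values.

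**1. Definition against schedule**

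| Part of the SAP window | Scheduled source |
|---|---|
| Ongoing at Study Day 1 | Baseline row of Table 1 |
| Started from Study Day 1 to last dose: anticancer treatment and supportive care | Breast cancer treatment row, footnote 3 |
| Started from Study Day 1 to last dose: any other drug | None |
| Started in the 28 days after last dose: anticancer treatment and supportive care | Same row, footnote 3 |
| Started in the 28 days after last dose: any other drug | None |

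**2. Is the single baseline mark a layout slip?** It does not look like one. In the same table, ECOG, CBC and adverse events are marked at baseline and during treatment, and breast cancer treatment in all three periods. The row label and Protocol Section 8.3 both carry the word baseline as well.

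**3. Other possible sources.** Protocol Section 8.4.1 has sites transcribe chart data after each visit but does not name concomitant medications. The safety follow-up in Protocol Section 10 covers selected events only and is described as going beyond what the eCRF holds. Neither is named as a source for the SAP output. Nor does the SAP say whether the supportive-care entries feed it.

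**4. Illustrative size, for drugs outside the supportive-care entry.** Let b be the share of patients on a drug class at baseline and s the share of the remainder who start it later. Both are assumptions; neither is in the documents.

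- True ever-use = b + (1 − b) × s
- Reported use = b
- Shortfall = (1 − b) × s

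| b | s | True ever-use | Reported | Shortfall (points) |
|---|---|---|---|---|
| 40% | 5% | 0.40 + 0.60 × 0.05 = 43% | 40% | 3 |
| 40% | 10% | 0.40 + 0.60 × 0.10 = 46% | 40% | 6 |
| 5% | 5% | 0.05 + 0.95 × 0.05 = 9.75% | 5% | 4.75 |
| 5% | 50% | 0.05 + 0.95 × 0.50 = 52.5% | 5% | 47.5 |

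The loss is small for long-term drugs already in use at enrolment and large for drugs mostly started on treatment. For supportive care it could be near zero, provided the footnote 3 entries are made and used.

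**The case against.** **The SAP definition is only a date rule.** It classifies whatever records exist, and the SAP gives no table shell, denominator or claim of complete capture. That is fair as far as it goes. But the SAP says all concomitant medications are coded, and its general methods report discrete variables as counts and percentages. Output produced under this definition carries the definition's period unless it is labelled otherwise.

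**The eCRF may be wider than Table 1.** It is not among the documents, so this stands as a possibility. It is why one cannot say that later starts are captured at 0%, only that none is scheduled. If the eCRF is wider, the source still has to be named and the schedule aligned.

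**Later medication is not wholly missed.** This stands. A reader might infer from the row label that nothing is collected after baseline; footnote 3 contradicts that. Supportive care is not defined, so an antibiotic started in month 2, for example, might fall under it.

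**The safety analysis is untouched.** This also stands. A reader might infer damage to the adverse-event results, because Protocol Section 10 lists drug interactions among possible sources of adverse events and makes "significant additional concomitant drug treatment, or other therapy" part of one criterion for reporting an abnormal test finding as an adverse event. Sites apply that criterion with the chart in front of them, and SAP Section 8.8.1 uses no concomitant-medication variable.

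**Conclusion.** The SAP's definition and the collection schedule do not match, and the SAP contradicts its own Table 1 as well as the protocol's. If both are followed as written, the concomitant-medication output, including the part for medications of interest, understates post-baseline use outside supportive care.

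The amount is unknown and depends on the drug class. A reader might infer that on-treatment use will come out far too low across the board. The documents do not support that, because they give no rates, and the 3 to 47.5 point range above rests entirely on assumed values of b and s.

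The stakes are limited. The output is descriptive, and concomitant medication is neither a listed objective nor an endpoint. rwTR, rwPFS, OS and the adverse-event analysis are unaffected. The conclusion assumes that the eCRF follows Table 1. It deserves correction because the output would otherwise be mislabelled and the correction costs almost nothing.

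**What to change.** In SAP Section 8, limit the concomitant-medication definition and output to medications ongoing at baseline and title it *baseline concomitant medications*. Report on-study supportive care separately, from the breast cancer treatment data. Apply the same limit to the medications of interest. The cost is SAP wording and a table title.

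Keep the window to 28 days after the last dose only if the eCRF already collects medications started after baseline. In that case, name that source in the SAP and align Table 1 in both documents.

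New on-treatment collection should not be assumed to be cheap. The SAP refers to COVID and to 2020 statistics, while the protocol's milestones put data collection from 16 December 2016 to 16 December 2021. Adding the item that late could mean a protocol amendment and retrospective chart abstraction for up to about 1,500 patients at about 110 sites (100 in the US plus 10 in Canada).
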